1. BACKGROUND AND SIGNIFICANCE

An increasing number of people is interested in consuming either grass-fed beef or plant-based beef alternatives, such as the Impossible BurgerTM or Beyond MeatTM, believing that these choices are beneficial for consumer health; however, little to no work has been performed to study these beliefs and claims. The *purpose of this study* is to evaluate effects of plant-based meat, grass-fed beef, and grain-fed beef on postprandial plasma inflammatory and metabolite profiles in middle aged adults (30-60 y old). This work will offer new insight into manipulating the acute, post-meal inflammatory state by consumer food choices. It will also provide more insight how food-derived metabolites impact systemic metabolites in the human body through metabolomics analysis. This study will utilize a randomized cross-over design and every participant will consume each type of meat on three separate occasions separated by a minimum of three days.

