Metabolic visits (Weeks 2-4. Number of Visits: 3. Duration: 7 hours each): These three visits will take approximately 7-hours each and will take place at The Center for Human Nutrition Studies (CHNS). Visits will be at least 3 days apart. Participants are required to fast for 12 hours prior to reporting to the laboratory. During this, participants will complete the following:

- Meat consumption: Using a randomized cross-over design, participants will ingest 250 g (9 oz) of an Impossible BurgerTM burger (plant), a grain-fed beef burger (grain-fed), a grass-fed beef burger (grass-fed). The meat will be stored as 9 oz. (250 g) patties in designated food freezers (-40 °C) in the NDFS kitchen and thawed overnight in a refrigerator (4 °C) prior to the subject's arrival the next morning. The meat will be cooked on a griddle in the CHNS metabolic kitchen on each side until an instant-read meat thermometer registers an internal temperature of 160 °F (71 °C). The patties will then be immediately served to the participant. Participants are provided with a standardized amount of water (1.5 liters) to drink during the 300 min post-meal phase. Participants will be asked to eat and drink the water at a comfortable rate but to try and finish within 30 min. No other food is allowed to be consumed during the ensuing 300 min postprandial phase. No other liquids are allowed to be consumed during that time as this would interfere with our protocol (see urine collection below). Subjects are also expected to remain seated in a chair during this time and can work/read/or watch entertainment on their own electronic device. Participants will be allowed to get up and use the rest-room; however, we will ask participants to remain sedentary otherwise.
- o **Blood Draws:** An intravenous catheter (IV) will be temporarily placed into a forearm or hand vein by a trained member of the study team (the PI) to collect repeated blood samples. The catheter will remain viable by a slow drip of saline. We will collect four samples total (10 mL each; 40 mL or 2 ½ tablespoons) on each of the three metabolic visits. One sample will be collected right before participants eat and three more samples will be collected at 60, 180 min and 300 min after they consume the meal. These draws will be taken in a private room in clinical facilities, in a reclining leather chair. Participants will be provided with their

Version 1 Page 5 of 9

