7. ANALYTICAL PROCEDURES AND STATISTICAL CONSIDERATIONS

- o **Inflammation:** Inflammatory biomarkers (IL-6, VCAM-1, TNF-alpha and C-reactive protein [CRP]) will be measured using ELISA kits at Dr. [name]'s laboratory at Utah State University. Plasma samples will be stored at -80°C until cytokine analyses are performed.
- Metabolomics: Mass spectrometry techniques will be used for untargeted and/or targeted assessment of blood and/or urinary metabolites. This analysis will give insight into the appearance of food-derived metabolites in the human body and how they may impact inflammatory responses after eating. This analysis will be performed using de-identified samples by Metabolon Inc (a company dedicated to metabolomics analysis) and/or the Plant for Human Health Institute. Samples will be provided to these core services as de-identified samples. No other data will be shared with these core services. Plasma and urine samples will be stored at -80°C until metabolomics analyses are performed.

Version 1 Page 7 of 9

- o **Dietary logs:** The Diet History Questionnaire III (NIH) and 3-day food records will be analyzed by dietetic staff within Dr. [name]'s laboratory at Utah State University.
- Statistical analysis: Change scores (post-dietary intervention baseline) will be created for all inflammatory biomarkers and metabolites. Metabolic intermediate data will be reduced into Metabolic Factors using Principal Component Analysis (PCA) of the change scores. Factor scores will be computed for each individual for both diets. Change scores and factor (change) scores for both diets will be compared using paired t-tests. P< 0.05 will be considered statistically significant and analyses will be performed in SAS 9.4 (SAS, Cary, NC).

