- o **Power Calculations:** Using untargeted metabolomics for our power calculations of the number of participants we need to recruit, we assume a P-value ≤ 0.05, Q-value ≤ 0.3, and standard deviation of 0.3 based on previous work (Pimentel et al., 2018). Since there are no entirely comparable previous studies available to draw from, the effect size and number of truly different metabolites are meant to give general estimates. 600 metabolites are typically identified (Nieman et al., 2015) and conservative estimation is that 20-40 metabolites will be significantly different with a mean of 0.2624 (30% difference). An n=24 per group is expected to provide true discovery rates ranging from 89-93 % assuming differences in 80-120 metabolites. Assuming a drop-out of 20%, the final number of participants we will recruit is N=30. This, we consider adequate without having to engage more participants than necessary to address the research aims.

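### No set of meal orders is specified and the paired t-tests carry no visit term, so any visit effect on the post-meal response costs precision and, in an unlucky draw of orders, distorts a burger contrast

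*Combined protocol and SAP*

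**What the plan says.** Section 1 of the combined protocol and SAP states: "This study will utilize a randomized cross-over design and every participant will consume each type of meat on three separate occasions". Section 3.3 (Meat consumption) repeats that the crossover is randomised and names the three burgers. Neither place, nor any other, lists the orders, says whether they are balanced, or describes how the allocation is made. On spacing, Section 3.3 says "Visits will be at least 3 days apart", and its visit table gives 3 to 7 days.

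Section 7 (Statistical analysis) gives the outcome scale: "Change scores (post-dietary intervention baseline) will be created for all inflammatory biomarkers and metabolites". Section 3.3 provides a pre-meal blood sample and a pre-meal urine sample at each visit. The comparison is then: "Change scores and factor (change) scores for both diets will be compared using paired t-tests", with "P< 0.05 will be considered statistically significant". There is no term for visit or order, and the sentence is written for two diets although there are three burgers.

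**The concern.** A paired t-test removes stable differences between people. It does not remove differences between visits. If visit 1 differs from visits 2 and 3 in the post-meal course, a participant's difference between two burgers includes the visit effect whenever one of those two burgers came first.

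The schedule gives some reason to expect this. Visit 1 is the first metabolic visit with a catheter and a 300-minute seated stay. At the shortest allowed spacing, the three logged days before visit 2 include visit 1 itself, and nothing comparable precedes visit 1.

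Two things are at stake: the precision of every burger contrast, and the reading of the one allocation that is realised if the orders fall unevenly. The order list has to be fixed before enrolment. The visit term can be pre-specified at almost no cost.

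**Working it through.** **Inputs from the documents.** 24 completers and 20% drop-out (Sections 4.1 and 7); three burgers, one per visit (Sections 1 and 3.3); significance level 0.05 (Section 7), taken as two-sided because sidedness is not stated. The plan's recruitment figure reproduces: 24 / (1 − 0.20) = 30.

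**Assumed.** A shift at visit 1 only, of f within-person SDs, on the change score, where σ is the within-person SD of a change score at one visit. The documents give no value for f, so 0.25, 0.5 and 1 are shown.

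**Standard error of the paired test.** Let I_A and I_B mark which burger came first. The difference A − B gains fσ(I_A − I_B), which is +fσ, −fσ or 0, each for one third of participants, with variance (2/3)f²σ². So

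Var(A − B) = 2σ² + (2/3)f²σ² = 2σ²(1 + f²/3), and the SE factor is √(1 + f²/3).

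- f = 0.25: √1.021 = 1.010, about +1%
- f = 0.5: √1.083 = 1.041, about +4%
- f = 1: √1.333 = 1.155, about +15%

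The SE without a visit effect is √(2/24)σ = 0.289σ; at f = 1 it is 0.333σ.

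**If orders are drawn freely.** Let k be the number having A first minus the number having B first. Then SD(k) = √(24 × 2/3) = 4, so SD(k/24) = 0.167. |k| is 6 or more (25 percentage points) in about 17% of trials, and the 95th percentile of |k|/24 is 33 points. Given k, the contrast shifts by fσk/24. At k = 6 that is 0.0625σ, 0.125σ and 0.25σ for the three values of f.

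Over all draws the mean shift is zero. Its variance, f²σ² × 0.167², equals f²σ² × (2/3)/24, which is the same term as the added variance above. The chance shift and the larger SE are therefore one quantity, to be counted once. Simulated trials at n = 24 give:

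| f | Type I error, all free draws | Type I error, free draws with \|k\| ≥ 6 | Type I error, six orders × 4 |
|---|---|---|---|
| 0.25 | about 5% | about 5% | about 4.7% |
| 0.5 | about 5% | about 7% | about 4.0% |
| 1 | about 5% | about 11 to 12% | about 2.5% |

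**If orders are balanced.** k = 0, so the contrast does not shift and its true SD stays at 0.289σ. The paired t-test still reports the inflated SE, which is why its type I error falls below 5%. Balance alone does not recover the precision; the visit term does.

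**Dependence on the meaning of the planned SD.** Section 7 assumes an SD of 0.3 without saying whether it is per visit or of the within-person difference. If per visit, shifts of 0.15 and 0.30 are f = 0.5 and 1, as above. If it is the SD of the difference, the same shifts give variance factors 1 + (2/3)(0.15²)/0.09 = 1.167 and 1 + (2/3)(0.30²)/0.09 = 1.667, so the SE rises by 8% and 29%. On that reading, with free orders, simulated power of one paired test for the planned difference of 0.2624 falls from about 98% to about 97% and 89%. With the visit term it stays at about 98%.

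**The case against.** - **The plan is silent on orders; it does not reject balance.** A reader might infer that the orders are unbalanced. The documents do not support that, because an unreported balanced list fits the wording equally well. This stands, and it is why both cases are worked out above.
- **Randomisation already protects the test.** A reader might infer that the contrasts are biased or that false positives are inflated in general. They are not: with free orders the average bias is zero and type I error is near 5%, and with balanced orders the test is conservative. What remains is lost precision, and distortion conditional on a poor draw. Even then, the 0.25σ shift at k = 6 and f = 1 is smaller than one SE (0.289σ with no visit effect, 0.333σ at f = 1).
- **The controls are good.** A 12-hour fast, fixed water, seated rest, replicated food and sleep, and a same-day baseline all make visits more alike. The change score cancels any visit shift that is equal before and after the meal. Only an effect on the post-meal course is left, its size is unknown, and at 0.25 SD the cost is about 1%. This limits the size of the point but does not remove it.
- **Satiety.** It has no pre-meal rating, so a reader might cite it as the clearest casualty. Section 7 applies the paired t-tests to change scores and factor scores of biomarkers and metabolites and states no satiety analysis, so this test cannot be faulted on that ground.

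**Conclusion.** The point holds as a weakness in the analysis, with a gap in the stated allocation. The plan specifies no meal orders, and its paired t-tests have no visit term. Under an assumed first-visit effect of 0.25, 0.5 or 1 within-person SD on the post-meal change, the reported SE is about 1%, 4% or 15% larger than it need be. Type I error is about right on average with free orders, raised in the roughly one trial in six with a marked imbalance for a given pair of burgers, and below nominal with balanced orders. The visit term helps in all of these cases.

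The conclusion rests on 24 completers, a shift confined to visit 1, normally distributed change scores, and effect sizes that the documents do not supply. If there is no visit effect on the post-meal response, nothing is lost under the present plan. The sample size does not depend on this point.

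**What to change.** **Section 7.** Replace the paired t-tests with a within-person model of the change scores, and likewise of the factor scores, with burger and visit number (1, 2, 3) as fixed effects and participant as a random effect. Estimate all three burger contrasts from it. This also corrects the wording for two diets.

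**Section 3.3.** State that participants are randomised to the six possible burger orders in blocks of six: 30 / 6 = 5 per order at enrolment. Completers would be 24 / 6 = 4 per order only if drop-out is even. The visit term handles the imbalance if it is not.

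**Cost.** One allocation list and a rewritten sentence; no added visits or participants, and N = 30 stands. The visit term uses two degrees of freedom: with 24 completers and 72 change scores, the residual goes from 72 − 24 − 2 = 46 to 44. If there is no visit effect and orders are unbalanced, the SE is on average about 2 to 3% larger than without the term, and more in a badly unbalanced draw; blocking keeps this loss small. The model pools the residual variance across burgers, so the plan should say that this will be checked.

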2. STUDY OBJECTIVES

- To determine the effects of consuming 9 oz of the Impossible BurgerTM, grass-fed beef or grain-fed beef on 300 min postprandial plasma inflammatory markers (IL-6, TNF-α, C-reactive protein, and VCAM-1).
- o To determine effects on plasma metabolites (vitamin and mineral derivatives, phenolics, amino acids etc.) collected through regular urine sampling during the 300 min postprandial phase (at 60 min, 180 min, and 300 min).
- o To determine the effects on subjective satiety at 30, 60, 90, and 120 min and every hour thereafter following consumption.

3. DESIGN AND PROCEDURES

3.1 Study duration

The study timeline for this protocol is a minimum of 3-4 weeks depending on participant and study staff availability.

3.2 Participants

We will include up to 40 middle aged adults (30-60 years) in this study. Inclusion/exclusion criteria are listed below.

Inclusion criteria:

- Age \ge 30 and \le 60 years;
- BMI \geq 25 and \leq 35 kg/m²;
- Weight stable in last 3 months (Loss or gain <4%);
- Hemoglobin A1C (HbA1C) ≤6.4%;
- Fasting plasma glucose concentration <126 mg/dl;
- For the safety of the participant and proper consent of the procedures, subjects must be able to speak and understand English to participate in this study

Version 1 Page 2 of 9

Exclusion criteria:

- Use of medications that are known to affect the study outcome measures (e.g., NSAIDs, corticosteroids) or increase the risk of study procedures (e.g., anticoagulants) that cannot be temporarily discontinued for this study;
- Consuming >14 drinks per week;
- Use of cigarettes (or other tobacco products) in last 3 months;
- COVID vaccine within the last two weeks;
- Engaged in high-level competitive exercise (e.g., triathlon, marathon, powerlifting);
- Any inflammatory diseases (e.g. autoimmune diseases, coeliac disease glomerulonephritis, hepatitis, inflammatory bowel disease, arthritis);
- Diagnoses of active malignancy, congestive heart failure, diabetes mellitus and/or chronic obstructive pulmonary disease;
- Use of antibiotics in last 60 days;
- Pregnant or planning to in the next month*;
- Lactating women;
- Soy allergy;
- Persons who are unable or unwilling to follow the study protocol or who, for any reason, the research team considers not an appropriate candidate for this study, including non-compliance with screening appointments or study visits.

3.3 Study Schedule

Participants will be asked to complete one screening/consent visit and three testing visits throughout their participation in the study. All visits will take place in clinical research space located at the Center for Human Nutrition Studies (CHNS). The research team will accommodate the availability of the research participants, including weekend days if needed. The table below describes these activities.

Visit	Timepoint	Activities	Location	Duration
Phone Screen	Week 1	- Pre-screening questions to	Virtual	15 min
		determine eligibility.		
Consent	Week 1	- Consent (online or in person)	Virtual or CHNS	1 hour
Screening	Week 1	Height/weightBlood drawScreening questionnaires	CHNS	1 hour
Metabolic visit (3 visits separated by	Week 2-4	IV PlacementEat study provided mealPostmeal phase (300 min)	CHNS	7 hours each
3-7 days)		- Regular urine and blood collection		

Version 1 Page 3 of 9

^{*} Participants that are pregnant or planning on becoming pregnant in the next month are excluded. The justification is the documented alterations in metabolism that occur during pregnancy (Lain and Catalano, 2007), which would impact our metabolomics analysis in this study.

Phone Screen (Week 1. Duration: 15 min): Interested participants will be pre-screened by telephone, using a scripted list of questions (see attached) to identify individuals that may be eligible for study entry. Suitable candidates will then be provided a REDCap survey link to complete additional screening questions that asks them further details about their health, dietary habits, and sleep habits (see inclusion/exclusion criteria). Only the minimum PHI will be collected to determine eligibility. Responses will be reviewed by a study team member (all study team members will have completed the necessary CITI training) and potentially eligible candidates will be contacted to schedule a consent/screening visit. The pre-screen is put in place to confirm that the participant meets most of the inclusion/exclusion criteria before the subject is scheduled for a consent meeting. The phone screen is thus performed to limit the amount of ineligible research participants that are consented/screened that could easily be excluded by means of a phone screening. This would also provide interested participants with the opportunity to ask additional questions about the study and to determine if they are interested in moving forward with a consent/screening visit. This will limit both subject and research staff time burden.

Consent Visit (Week 1. Duration: 1 hour): This visit can be done virtually through Zoom or occur in person in the Center for Human Nutrition Studies (CHNS) at Utah State University. Potential subjects will attend a consent session conducted by a trained member of the research staff to present the details of the study. Interested participants will complete the informed consent process privately with study staff. We will allow up to 60 minutes for the subjects to read the consent and ask questions. If a subject wants additional time to think about the study, this will be allowed. The study team will contact the subject three days after the initial consent visit ask if he or she has come to a decision. No study procedures will take place before written consent is obtained. To minimize subject burden, participants will be instructed during the phone screen that they have to opportunity to combine the consent visit with their screening visit (see below). If participants wish to combine visits, they are instructed that they will have to perform this visit in the morning after an overnight, 12-hour fast.

Screening Visit (Week 1. Duration: 1 hour): This visit will take place at the Center for Human Nutrition Studies (CHNS) and will last approximately 1 hour. We ask participants to come in during the morning after an overnight, 12-hour fast. During this visit the following procedures will be performed:

- o **Blood Draw:** A trained phlebotomist (the PI) will draw a fasted blood sample for routine blood work (see table 2 below) to ensure the participant qualifies for the study. Using a small needle, 12 ml blood will be collected from a vein in the participant's forearm or hand. Blood samples will be sent to LabCorp to be analyzed for HbA1C, Glucose, Basic Metabolic Panel (BMP), and Lipid panel. The blood of women of childbearing potential will be subject to a pregnancy test (hCG) as part of this screening blood draw. This will also occur through LabCorp.
- Body mass and height. Height (cm) will be measured without shoes. Body mass (kg) will be measured without shoes, coats, or sweaters. BMI will be calculated as body mass (kg) / height (m)².

Version 1 Page 4 of 9

- o **Blood pressure:** A blood pressure measurement will be taken using an automated upper arm blood pressure monitor (Omron BP5250). A total of three measurements will be taken and the average value of those will be collected for participant characterization.
- Questionnaires: Participant will be given a three-day food and sleep log to fill out for three days prior to each of the metabolic visits described below. The participant will also be given a food frequency questionnaire once at the beginning of the study, which will ask them about how often they consume animal products and if they are any of the following: "grass-fed, organic, pasture-raised, or bought on a farmers market". This will give us an indication of the habitual consumption of pasture-raised animal products of the participants. The food frequency questionnaire that will be used is a modified version of the Diet History Questionnaire III (NIH) with a 5-point ordinal scale as adapted from Baudry et al. (2015) (see attachment). The questionnaire reviews food and beverages typically consumed over the past year and takes approximately 30 minutes to complete.

Metabolic visits (Weeks 2-4. Number of Visits: 3. Duration: 7 hours each): These three visits will take approximately 7-hours each and will take place at The Center for Human Nutrition Studies (CHNS). Visits will be at least 3 days apart. Participants are required to fast for 12 hours prior to reporting to the laboratory. During this, participants will complete the following:

- Meat consumption: Using a randomized cross-over design, participants will ingest 250 g (9 oz) of an Impossible BurgerTM burger (plant), a grain-fed beef burger (grain-fed), a grass-fed beef burger (grass-fed). The meat will be stored as 9 oz. (250 g) patties in designated food freezers (-40 °C) in the NDFS kitchen and thawed overnight in a refrigerator (4 °C) prior to the subject's arrival the next morning. The meat will be cooked on a griddle in the CHNS metabolic kitchen on each side until an instant-read meat thermometer registers an internal temperature of 160 °F (71 °C). The patties will then be immediately served to the participant. Participants are provided with a standardized amount of water (1.5 liters) to drink during the 300 min post-meal phase. Participants will be asked to eat and drink the water at a comfortable rate but to try and finish within 30 min. No other food is allowed to be consumed during the ensuing 300 min postprandial phase. No other liquids are allowed to be consumed during that time as this would interfere with our protocol (see urine collection below). Subjects are also expected to remain seated in a chair during this time and can work/read/or watch entertainment on their own electronic device. Participants will be allowed to get up and use the rest-room; however, we will ask participants to remain sedentary otherwise.
- o **Blood Draws:** An intravenous catheter (IV) will be temporarily placed into a forearm or hand vein by a trained member of the study team (the PI) to collect repeated blood samples. The catheter will remain viable by a slow drip of saline. We will collect four samples total (10 mL each; 40 mL or 2 ½ tablespoons) on each of the three metabolic visits. One sample will be collected right before participants eat and three more samples will be collected at 60, 180 min and 300 min after they consume the meal. These draws will be taken in a private room in clinical facilities, in a reclining leather chair. Participants will be provided with their

Version 1 Page 5 of 9

clinical lab results that will be obtained from LabCorp. Results from bloodwork will be shared with participants via encrypted email using a USU email account.

- O Urine Collection: A baseline urine sample will be collected prior to food consumption. Participants are asked to completely empty their bladder prior to food consumption. After food consumption, all urine will be collected in a urine jug (a 3000 mL urine collection bottle) during the 300-minute postprandial phase to study metabolites in the urine. All urine collections will be done by the participant themselves in private restroom facilities.
- Satiety Scale: Participants are asked to mark a satiety scale (Holt et al., 1995) at 30, 60, 90, 120 min, and every hour thereafter until 300 min to assess subjective satiety after meat consumption.

Dietary and activity control: We will ask participants to maintain their habitual diet, physical activity, and sleep levels. We will ask participants to fill in 3-day dietary and sleep logs for the three days prior to their metabolic visit (see attachments). We will also ask them to refrain from alcohol and strenuous physical activity (running, weightlifting etc.) for 2 days prior to each metabolic visit. The dietary and sleep logs will give us insight if lifestyle factors leading up to each visit were similar and are likely to promote compliance to ensure robust biomarker results (inflammatory cytokines and metabolomics). Participants are asked to replicate their 3-day foods logs and sleep schedule as much as possible prior to each visit. Participants are also asked to not consume red meat or soy (main ingredient of plant burger) the day before each visit. This is done to minimize any prior presence of common red meat and soyderived metabolites in the urine.

Table 2. Schedule of sample collection

Lab/Blood Work	Screening	Met Visit 1	Met Visit 2	Met Visit 3
Pregnancy test (hCG)	X			
Insulin	X			
Glucose	X			
BMP	X			
Lipid panel	X			
HbA1C	X			
Blood inflammatory markers		X	X	X
Urinary/plasma metabolomics		X	X	X

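### The protocol describes no masking of which beef burger is served, although satiety is self-rated; a kitchen-held code for the two beef patties would reduce the risk of expectation bias at little cost.

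*Combined protocol and SAP*

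**What the plan says.** Section 3.3 (Meat consumption) sets out the design: "Using a randomized cross-over design, participants will ingest 250 g (9 oz") of each product. The two beef conditions are "a grain-fed beef burger (grain-fed), a grass-fed beef burger (grass-fed"). Both are patties of the same weight, frozen at -40 °C, thawed overnight at 4 °C and griddled to 71 °C. The serving step reads: "The patties will then be immediately served to the participant". It does not say who knows which patty it is.

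Section 2 lists subjective satiety last among the objectives, to be assessed "at 30, 60, 90, and 120 min and every hour thereafter following consumption". Section 3.3 (Satiety Scale) makes it a self-rating: "Participants are asked to mark a satiety scale". No pre-meal rating is listed.

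Section 1 says that people choose grass-fed beef or plant-based alternatives "believing that these choices are beneficial for consumer health". The food frequency questionnaire given at the start of the study (Section 3.3, Screening Visit) asks whether the animal products participants eat are "grass-fed, organic, pasture-raised, or bought on a farmers market".

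The inflammatory markers "will be measured using ELISA kits" (Section 7). Samples are stored under coded labels (Section 8) and sent de-identified for metabolomics (Section 7). Neither measure is stated to hide the meal.

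**The concern.** A self-rating is the kind of outcome most easily moved by knowing what one has eaten. The trial is motivated by beliefs about these products, and its questionnaire draws participants' attention to the grass-fed attribute before the first test meal. If participants know which beef they are eating, any difference in their ratings mixes the effect of the meat with the effect of its label.

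Randomising the order does not help. It balances period effects, but a label effect travels with the meal in every period. Nor can the analysis recover what was lost, so masking has to be settled before meals are served. At stake is the grass-fed versus grain-fed satiety comparison, the one place where masking of participants looks practicable.

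**Working it through.** **1. The plan's own figure.** Section 7 (Power Calculations) takes 24 completers and 20% drop-out: 24 / (1 − 0.20) = 30, which matches the stated recruitment number. Masking changes neither 24 nor 30.

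**2. Is masking described anywhere?** Reading the available text from Section 1 to Section 10:

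| Place | What is coded or hidden | Does it hide the meal? |
|---|---|---|
| 3.3 Meat consumption | nothing | no |
| 3.3 Satiety Scale | nothing | no |
| 7 Metabolomics | samples de-identified for the outside laboratories | not stated |
| 8 Biospecimens, records | coded labels and participant codes, for storage and confidentiality | not stated |

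**3. Is a code feasible for the beef?** Weight, storage, thawing, cooking method and end temperature are the same for both beef patties. Nothing in the procedure requires participants or raters to know which is which. The plant burger is a different product and may be hard to disguise, so the proposal does not try.

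**4. How many ratings are exposed?** 30, 60, 90, 120, 180, 240 and 300 min: seven per visit.

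**5. What could a label effect do? (Illustration only.)**

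Inputs from the documents: n = 24 completers (Sections 4.1 and 7) and significance level 0.05 (Section 7).

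Assumptions: a two-sided paired t-test is applied to satiety; there is no true difference between the beef burgers; and the label shifts the mean paired difference by δ, in units of the SD of that difference. The documents give no value for δ, so a range starting at zero is shown.

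The test statistic follows a noncentral t distribution with 24 − 1 = 23 degrees of freedom and noncentrality δ × √24 = δ × 4.899. The false-positive rate is the probability that its absolute value exceeds the two-sided 5% critical value.

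| δ (SD) | Noncentrality | False-positive rate |
|---|---|---|
| 0 | 0 | 5% |
| 0.1 | 0.490 | 7.6% |
| 0.2 | 0.980 | 15.6% |
| 0.3 | 1.470 | 29.1% |
| 0.5 | 2.449 | 65.0% |

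The table shows how sensitive such a test would be to a label effect. It says nothing about whether one exists.

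**The case against.** The best case for leaving the plan alone has four parts.

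- **Satiety carries little weight.** It is the last-listed objective, is outside the power calculation, and is not named in the statistical analysis paragraph, which covers change scores of biomarkers and metabolites. This stands, and it limits the importance of the point.
- **The belief is not about satiety.** Section 1 reports a health belief held by consumers in general. It does not say that participants expect grass-fed beef to be more or less filling. This stands: the direction of any bias is unknown, and expectations that differ between participants would partly cancel.
- **The shift sizes have no source.** This also stands. The 65.0% figure is simply the power of a 24-pair test at 0.5 SD and needs expectations that push the same way on average.
- **Taste or appearance may reveal the patty.** This is possible, and the documents hold no data on it. It limits what a code achieves, but a code would still remove the explicit label.

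A reader might infer that the trial is declared open-label or that participants are told which beef they are eating. The documents say neither. They are silent, and the title and consent pages were not available for review. A reader might also infer that the inflammatory results are compromised. That does not follow: assay outcomes are much less exposed to expectation, samples already carry coded labels, and no re-run or outlier procedure is described through which knowledge of the meal would act.

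**Conclusion.** The point holds as an inexpensive improvement of moderate weight. The procedures describe no masking of the beef burgers, satiety is a stated and self-rated objective, and the two beef patties are handled identically up to serving. Followed as written, the plan leaves the grass-fed versus grain-fed satiety comparison open to label-driven expectation, and a code would reduce that.

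The size cannot be estimated from the documents. Over an assumed shift of 0 to 0.5 SD, the false-positive rate runs from 5% to 65.0%, and at 0.1 SD it is 7.6%. These figures rest on 24 pairs and on a paired t-test that the plan does not specify for satiety.

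It would be tempting to say that the bias falls on one of three planned contrasts, or that coding would largely remove it. The analysis paragraph names neither three contrasts nor satiety, and nothing in the documents measures how well a code would work.

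**What to change.** 1. In Section 3.3, label the two beef patties A and B under a code held by whoever prepares the meals.
2. State that participants, the staff collecting satiety ratings and the ELISA analyst are not told which beef was served until the database is locked. For the analyst this is a secondary safeguard; the existing coded sample labels can serve if they are stated to hide the meal.
3. State that satiety comparisons with the plant burger are open-label.
4. Optionally, ask participants after the beef visits to guess which beef they ate, to show how far the masking held.

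The cost is a code list and a few sentences in the protocol; the sample size stays at 24 completers and 30 recruited. There are two downsides. Taste may partly unmask participants. The person preparing the meals should not also collect the ratings, which may need a division of roles that the protocol does not yet describe.
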